2 INTRODUCTION

2.1 STUDY RATIONALE

Total joint arthroplasty can result in significant blood loss. Bone wax is a well-known topical hemostatic agent comprised of a mixture of beeswax, paraffin, and isopropyl palmitate. This inexpensive agent works by sealing the bleeding site and tamponades bleeding from the exposed cancellous bone.²

The purpose of this study is to assess whether the application of bone wax to the exposed cancellous bone, after the cemented implants are in place, will provide superior hemostasis in a total knee arthroplasty patients compared to patients who do not have the bone wax applied. Hemostasis will be assessed by calculating blood loss using the Hb-balance formula.

This will be a prospective, randomized, single-blinded, superiority study in patients scheduled for a primary unilateral TKA with [name] or [name]. The restriction of this study to two surgeons will limit variations in the outcomes being measured due to differences in surgical technique. The application of bone wax to the exposed cancellous bone has been the standard of care for four years by Drs. [name] and [name]. The surgeons technique is to apply the bone wax to the exposed cancellous bone after the implant has been cemented in place thereby eliminating the risk for any issues with bone ingrowth.

2.2 BACKGROUND

Postoperative anemia has also been associated with prolonged length of stay and increased hospital costs.¹ In order to minimize blood loss, multiple blood conservation strategies have been developed for orthopaedic procedures. One method of hemostasis in use at Syosset hospital since March 2013 is the use of intravenous antifibrinolytics (tranexamic acid). Tranexamic acid (TXA) interferes with clot breakdown. The administration of tranexamic acid has been associated with a significant reduction of postoperative bleeding and blood transfusions in patients undergoing total joint arthroplasty and has become a well-established practice in orthopaedic surgery. Porter, et al in a 2020 retrospective chart review of 38,220 patients administered intravenous tranexamic acid (IV TXA) found no significant difference in the odds of adverse outcomes (PE,DVT, MI,CVA) between high-risk patients who received TXA and high-risk patients who did not receive TXA. However, one of the limitations of the study was that high-risk patients who did not receive TXA had a higher baseline incidence of risk factors such as DVT,PE, MI, and CVA compared to the high risk patients who did receive TXA.³ This manuscript was the basis for the current departmental protocol for the administration of TXA. As per this protocol IV TXA is typically not administered to patients with multiple risk factors for thromboembolic events and they are instead given intra-articular TXA by the orthopaedic surgeon. Patients excluded from IV TXA will not be enrolled in this clinical trial so as to eliminate any confounding factors. (Appendix A-Total Joint Arthroplasty Pharmacologic Protocols)

Epidural or spinal anesthesia (neuraxial blockade) has been shown to be effective in reducing intraoperative blood loss. Rodgers, et al in a meta-analysis of 473 patients in 16 trials reported the requirement for a transfusion of two or more units of blood was reduced by about half in patients allocated to neuraxial blockade.⁴ Spinal or epidural anesthesia causes a sympathetic nerve block leading to vasodilatation distal to the site of anesthesia this effect is responsible for the reduction in bleeding during surgery.

Another method used intraoperatively to maintain hemostasis is the application of a pneumatic tourniquet. During TKA, a pneumatic tourniquet is applied to the upper part of the thigh on the operative limb and inflated to a pressure determined by the surgeon. The tourniquet applies pressure to the limb to occlude the blood supply. The tourniquet is released by the surgeon at the end of the case and electrocautery is then used to seal any bleeding vessels.

Significant blood loss intraoperatively and post-operatively can produce complications. The use of hemostatic agents such as bone wax may further facilitate hemostasis during a total knee arthroplasty. Bone wax was developed in 1885 by a British neurosurgeon named Sir Victor

Horsley. Bone wax consists of beeswax, paraffin and isopropyl palmitate. Since its first documentation of hemostatic potential in 1892, there has been a number of modifications to its formulation.² The main component that remains is beeswax. Today bone wax is used in a variety of surgical procedures as a mechanical hemostatic agent. During total joint arthroplasties bone wax is softened and applied firmly on the cancellous bone around the prostheses.

Bone wax increases hemostasis because of its ability to immediately seal and plug marrow sinusoid and consequently prevent oozing of blood.³ Studies have shown other benefits of bone wax, like the ability to decrease post-operative edema and pain.⁵ In the study conducted by Moo et al. 100 patients were recruited into a 1:1 randomization: (1) bone wax (2) control. Measurements were taken for height, weight, serum hemoglobin levels and base line lower limb diameters. Hemoglobin (Hgb) and Hematocrit (Hct) levels were checked on POD 1 and POD 3. Each study subject underwent total knee arthroplasty using standard procedures. Bone wax was applied around the prosthesis to obtain hemostasis in these areas. A significant decrease in blood loss was observed in the bone wax group at POD 1 and 3. None of the patients in the bone wax cohort required blood transfusions. Three patients in the control group required a blood transfusion.²

The limitations in the Moo et al. study were, they did not collect postoperative outcomes such as pain, range of motion, and Knee Society Score (KSS). Efficacy and safety data are lacking in this publication as most patients were transferred to a rehabilitation facility. Long term follow-up on clinical outcomes such as range of motion and functional assessment scores were not reported. The study subjects consisted of patients with osteoarthritis of the knee only, thereby, excluding whether patients with other inflammatory arthritis may benefit from the use of bone wax. The use of a chemical hemostatic agent tranexamic acid (TXA) was also excluded from the surgical procedure. The incorporation of TXA could have increased the level of hemostasis.

A recently published manuscript by Shin, et al also evaluated blood loss outcomes with the use of bone wax. Though this study also found bone wax reduced blood loss there were several limitations to the study. First, its retrospective design is inherently disadvantageous. Second, the postoperative outcomes such as pain score, range of motion, length of stay and clinical scores, were not compared between the groups. Third, although there was no significant intergroup difference in the radiologic prosthetic coverage of the osteotomy surface, the area of the cancellous bone surface uncovered by the femoral and tibial components were not evaluated intraoperatively. The area of residual osteotomy might be associated with the volume of blood loss and consequently with transfusion rates because osseous hemorrhage is one of the main bleeding sources.⁵

The investigators would like to address limitations in these studies by conducting a prospective, randomized trial. This study will also be collecting outcome measures (Knee Society Score) which were noted limitations of these studies. Additionally, the surgeons will be measuring the amount of exposed cancellous bone in the OR. The method to be used is referenced in this protocol.

2.3 RISK/BENEFIT ASSESSMENT

2.3.1 KNOWN POTENTIAL RISKS

The surgical techniques used to promote hemostasis will be consistent for all patients, except for the use of bone wax applied to the exposed cancellous bone following insertion of the prosthesis. There is a potential that patients in the control arm could have increase bleeding. The following risks have been shown to be associated with the use of bone wax: failed bone healing, foreign body reaction, granuloma growth, thrombosis, infection, and nerve compression

There is a small risk of an unintended breach of confidentiality, as there is in any research study that collects subjects' health information.

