8.3.4 TIME PERIOD AND FREQUENCY FOR EVENT ASSESSMENT AND FOLLOW-UP

The occurrence of an adverse event (AE) or serious adverse event (SAE) may come to the attention of study personnel during study visits and interviews of a study participant presenting for medical care.

All AEs including local and systemic reactions not meeting the criteria for SAEs will be captured on the appropriate case report form (CRF). Information to be collected includes event description, time of onset, clinician's assessment of severity, relationship to study product (assessed only by those with the training and authority to make a diagnosis), and time of resolution/stabilization of the event. All AEs occurring while on study must be documented appropriately regardless of relationship. All AEs will be followed to adequate resolution.

Changes in the severity of an AE will be documented to allow an assessment of the duration of the event at each level of severity to be performed. AEs characterized as intermittent require documentation of onset and duration of each episode.

At each study visit, the investigator will inquire about the occurrence of AE/SAEs since the last visit. Events will be followed for outcome information until resolution or stabilization.

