8.3.5 ADVERSE EVENT REPORTING

This clinical trial consists of postoperative total knee arthroplasty patients. DRE's common and expected in this group of patients include postoperative pain, nausea, hypotension, anemia, and dehydration. Events anticipated and expected in the postoperative arthroplasty patient will not be considered an adverse event for collection in the eCRF. Additionally, there are no study interventions for the control group. This group will be following the standard of care treatment for a total knee arthroplasty patient. Therefore, no adverse events related to the application of bone wax will be occurring in this group.

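### Increased bleeding is the risk named for controls, but no per-patient harm outcome is defined for it, and the adverse event rules conflict on whether anemia and hypotension are collected

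*Combined protocol and SAP*

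**What the plan says.** On the control-arm risk, section 2.3.1 states: "There is a potential that patients in the control arm could have increase bleeding". It names no other risk specific to that arm.

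On usual practice, section 2.1 says of the two participating surgeons: "The application of bone wax to the exposed cancellous bone has been the standard of care for four years". Section 8.3.5 says of the control group: "This group will be following the standard of care treatment for a total knee arthroplasty patient".

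On what is collected, section 8.3.5 gives disease-related events that are "common and expected in this group of patients include postoperative pain, nausea, hypotension, anemia, and dehydration", and then rules: "Events anticipated and expected in the postoperative arthroplasty patient will not be considered an adverse event for collection in the eCRF". It gives no severity threshold and does not separate the arms. Section 8.3.4 states: "All AEs occurring while on study must be documented appropriately regardless of relationship". Section 8.3.3.3 makes an event unexpected when its kind, severity or frequency departs from the risk information for the study intervention.

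On the safety objective, the synopsis and section 3 set out to compare safety between the two cohorts. The matching endpoint is device events related to bone wax. Section 9.4.4 reports adverse events descriptively.

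**The concern.** The objective is a comparison of safety between arms, but the rules mainly look for harm from applying wax. The harm the protocol foresees in controls is bleeding. Two of its clinical signs, anemia and hypotension, are examples of events not collected, and the remaining safety provisions are largely tied to the device.

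The trial could therefore report a blood-loss difference in mL and an uneventful safety table without saying whether any control patient needed treatment for bleeding. The synopsis justifies the trial by postoperative anemia, length of stay and cost, so a reader will want to know whether the mL difference mattered to patients. Because sections 8.3.4 and 8.3.5 point in different directions, two coordinators could also handle the same event differently.

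**Working it through.** The plan gives no figure on this point. The check is whether a bleeding event in a control patient has a defined route into the safety table.

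**Routes tied to the device**
- Safety endpoint (synopsis, section 3): bone-wax-related events. Section 8.3.5 says these will not occur in controls.
- Schedule of activities (1.3): the only adverse event row is for device events.
- Reporting period (8.3.1): begins when the wax is applied, so controls have no defined start.
- Serious events (8.3.2): deaths and serious injuries that the device may have caused or contributed to.
- Non-serious events (8.3.3.1): captured if felt to be related to the device.

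**Routes not tied to the device**
- Section 8.3.4 covers all adverse events whatever their cause. Section 8.3.5 then says expected postoperative events do not count as adverse events for the eCRF. Which rule governs anemia or hypotension is not settled.
- Section 8.3.3.3 lets unusual severity or frequency make an event unexpected. Its yardstick is the risk information for the study intervention, whereas 8.3.5 uses what is expected after arthroplasty. For a patient who received no wax, the two do not combine into a usable threshold.
- Section 8.1 allows the follow-up call, at about 56 days, to record other outcomes of relevance, but does not say which.

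**Bleeding as efficacy**
- Estimated blood loss on POD 1 is primary (9.1, 9.4.2). Hemoglobin and hematocrit change to POD 1 is secondary (9.1, 9.4.3).
- These compare group means. They do not identify patients who were treated for bleeding, and they stop at POD 1.
- Transfusion is foreseen (4.2, and exclusion 9 in 5.2) but is neither an endpoint nor a scheduled item.

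**Scale, as context only**
- The randomized bone wax study cited in section 2.2 had 100 patients allocated 1:1, with 3 transfused controls and 0 transfused bone wax patients. Taking 50 per arm (assumption):
  - controls 3/50 = 6% (exact 95% CI 1.3% to 16.5%);
  - bone wax 0/50 = 0% (upper limit 1 − 0.025^(1/50) = 7.1%);
  - two-sided Fisher p = 2 × C(50,3)/C(100,3) = 2 × 19,600/161,700 = 0.24.
- Chance of at least one event among 50 controls = 1 − (1 − p)^50. This is 39% at p = 1%, 64% at 2% and 95% at 6%. These rates are assumptions.
- Fisher power for 6% versus 0% with 50 per arm is about 8%. With no events on wax, significance needs at least 6 control events, and P(X ≥ 6) for a binomial with n = 50 and p = 0.06 is 0.078.

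Such events could plausibly occur and be listed, but a test of them would tell little.

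**The case against.** A reader might infer that the control-arm harm is never counted. The documents do not go that far. Section 8.3.4 requires all adverse events to be documented and has the investigator ask about them at each visit, and section 8.1 leaves room for other outcomes on the call. The plan conflicts with itself; it does not set one clear bar.

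A reader might also infer that anemia and hypotension are barred at any severity. That reads a rule into silence. Section 8.3.5 excludes expected events, and section 8.3.3.3 lets an unusually severe one count as unexpected. What stands is that 8.3.5 gives no limit and the two sections use different yardsticks.

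Nor does the 8.3.5 list by itself remove bleeding, hematoma, transfusion or reoperation, since it names none of them. Their lack of a place in the safety table comes from the device-tied endpoint, schedule and reporting period.

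It is also fair to say that bleeding is measured in every patient and formally compared, and that hemoglobin measures anemia directly. This answers the question of average blood loss, not whether individual patients came to harm.

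Reading sections 2.1 and 8.3.5 as flat opposites is too strong. One describes two surgeons' practice and the other general care for knee arthroplasty. They are in tension and need clarifying.

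Finally, the 3 versus 0 transfusions transfer poorly. Tranexamic acid was not used in that study (section 2.2), its transfusion difference was not significant (section 2.3.3), and this trial excludes patients who cannot receive it intravenously (section 5.2).

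**Conclusion.** The point holds as a gap in definition combined with conflicting collection rules. The protocol names increased bleeding as the control-arm risk and defines no per-patient harm outcome for it. Anemia and hypotension fall under an exclusion with no stated severity limit, which sections 8.3.3.3 and 8.3.4 partly contradict. Transfusion, hematoma and return to theatre for bleeding have no specified place in the safety table for the 50 controls. As written, the stated comparison of safety between cohorts cannot be relied on to register that harm.

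The documents do not fix the size in events. Under assumed control rates of 1% to 6%, the chance of at least one event in that arm is 39% to 95%. The blood-loss comparison and its power are unaffected.

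**What to change.** - Reconcile sections 8.3.1, 8.3.3.3, 8.3.4 and 8.3.5 on which events are collected, in which arm and at what severity. Start the reporting period at surgery in both arms.
- Limit the exclusion in 8.3.5 to events needing no treatment beyond routine care.
- Abstract from the hospital chart, in both arms from surgery to discharge: anemia or hypotension that led to treatment, transfusion, wound hematoma, and return to theatre for bleeding.
- Report these descriptively by arm in the final safety table under 9.4.4. At the 30- and 60-subject reviews in 10.1.6, show them pooled across arms only. Those reviews are specified as aggregate and section 4.1 plans no interim analysis, so a by-arm display would give an unplanned comparative look at outcomes tied to the primary endpoint.
- Clarify sections 2.1 and 8.3.5 on which arm departs from these surgeons' usual practice.

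The cost is a few extra data fields and one table, with no new test or visit. The counts will be too small to test and should be presented as a listing of harms.

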2.3.2 KNOWN POTENTIAL BENEFITS

Bone wax is used on cancellous bone to reduce blood loss during orthopaedic surgery. The incorporation of this hemostatic agent in standard TKA procedures could lessen the total blood loss intra-operatively and postoperatively for patients randomized to the study group.

Participating in this clinical study will contribute to current medical knowledge of this material. The results of this study can make a difference in the care of future patients by providing information about the benefits of these interventions.

2.3.3 ASSESSMENT OF POTENTIAL RISKS AND BENEFITS

Shin and Moo have published on the use of bone wax in total knee arthroplasty, 296 and 50 patients respectively had bone wax used during their total knee replacement. Shin, et al found that no adverse reactions, including the development of infections or foreign body reactions, were observed after the application of bone wax, a finding consistent with those of Moo et al.⁵

Moo found the difference between the bone wax group and the control group with regards to transfusion requirements and adverse events following surgery did not reach significance with the numbers available; however, trends in favor of the use of bone wax were noted.²

Drs. [name] and [name] have been using bone wax on exposed cancellous bone for over 4 years. All surgical site infections are reported as part of the Northwell Health System quality metrics. Bone wax has been used in 1140 total knee procedures. For this time period superficial

infections were reported in 2 patients and 1 deep infection. Additionally, the surgeons have not had any other issues felt to be related to the bone wax in their patients during their long term follow-up visits. The surgeons technique is to apply the bone wax to the exposed cancellous bone after the implant has been cemented in place therefore eliminating the risk for any issues with bone ingrowth.

3 OBJECTIVES AND ENDPOINTS

OBJECTIVES	ENDPOINTS	JUSTIFICATION FOR ENDPOINTS

Primary
 
• Efficacy: To assess whether bone wax results in superior hemostasis in patients undergoing primary unilateral TKA• Safety: To compare the safety profile between the 2 cohorts	
• To calculate estimated perioperative blood loss on POD 1 using the Hb-balance Formula• To assess the patients for any device adverse events related to the use of bone wax	
Use of the Hb-balance Formula provides a more accurate assessment of blood loss
 
To ensure there are no safety issues between the two cohorts

Secondary	
• To assess whether objective and functional outcomes in patients undergoing primary unilateral TKA differ between the two patient cohorts• To determine if there is a difference in blood loss between the two cohorts 
• To calculate the Knee Society Scores, both objective and subjective scores, done preoperatively and 8 weeks postoperatively• To measure the difference between the preoperative and POD1 Hemoglobin (Hgb) and Hematocrit (Hct) values in the two patient cohorts	
The Knee Society Score is a validated tool to assess both objective and subjective outcomes. The collection of the KSS is a standard of care for Drs. [name] and [name]'s TKA patients.
 
These values will be used to assess hemostasis over time

4 STUDY DESIGN

4.1 OVERALL DESIGN

- **A statement of the hypothesis:** The use of bone wax on exposed cancellous bone surfaces will provide superior hemostasis.
- **Phase of the trial:** NA. This study is using a FDA approved marketed product as per the package instructions.
- **A description of the type/design of trial to be conducted:** A prospective, randomized, single-blinded superiority study to evaluate bone wax use for hemostasis during primary unilateral total knee arthroplasty.
- **A description of methods to be used to minimize bias:** All patients scheduled for unilateral total knee arthroplasty will be approached for inclusion in the study.

- **The number of study groups/arms and study intervention duration:** This study will consist of 2 cohort groups. One group (50 patients) will have bone wax applied to the exposed cancellous surfaces of the bone (treatment group). The other group (50 patients) will serve as a control group. This study is a 1:1 allocation ratio. The patients will not be aware of their randomization assignment.
- **Indicate if single site or multi-site:** Single Site-Syosset Hospital Department of Orthopaedics
- **Name of study intervention(s):** Bone Wax
- **Note if interim analysis is planned and refer to details:** No interim analysis is planned.
- **Note if the study includes any stratifications:** Patient stratification is not needed for the randomization.
- **Name of sub-studies, if any, included in this protocol:** Not Applicable

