1 PROTOCOL SUMMARY

1.1 SYNOPSIS

Title:	A prospective, randomized, single-blinded superiority study to evaluate bone wax use for hemostasis during primary unilateral total knee arthroplasty
Study Description:	
Total joint arthroplasty can result in significant blood loss. Postoperative anemia has been associated with prolonged length of stay and increased hospital costs.¹ Minimizing blood loss has led to multiple blood conservation strategies in orthopaedic procedures.
 
Bone wax is a well-known topical hemostatic agent comprised of a mixture of beeswax, paraffin, and isopropyl palmitate. This inexpensive agent works by sealing the bleeding site and tamponades bleeding from the cancellous bone. Bone wax can be precisely applied evenly and stops bone bleeding immediately upon application.²
 
The purpose of this study is to assess whether the application of bone wax to exposed cancellous bone, after the cemented implants are in place, will provide superior hemostasis in total knee arthroplasty (TKA) patients compared to patients who do not have the bone wax applied. Hemostasis will be assessed by calculating blood loss using the Hb-balance formula.

	
This will be a prospective, randomized, single-blinded, superiority study in patients scheduled for a primary unilateral TKA with [name] or [name]. The restriction of this study to two surgeons will limit variations in the outcomes being measured due to differences in surgical technique.

Objectives:	
Primary Objective:
 
• Efficacy: To assess whether bone wax results in superior hemostasis in patients undergoing primary unilateral TKA• Safety: To compare the safety profile between the 2 cohorts 
Secondary Objective:
 
• To assess whether the objective and functional outcomes in patients undergoing primary unilateral TKA differ between the patient cohorts (use of bone wax vs no bone wax)• To assess if there is a difference in the reduction of the Hemoglobin (Hgb) and Hematocrit (Hct) between the patient cohorts

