6.1.2 DOSING AND ADMINISTRATION

Bone wax should be used immediately after removal from the package. Softened Bone Wax is applied to the bone edges as indicated by the surgical circumstances and the preference of the surgeon. Exposed cancellous bone surface can vary between patients. In order to capture this variance the surgeons will calculate the amount of exposed bone by the following method:

Once the distal femoral cut and prep for the chamfer cuts and notch cut is complete:

1. Measure the distal femur medial to lateral (ML) distance.
2. Measure the distance from anterior chamfer to most proximal portion of exposed anterior femoral bone.
3. Measure the ML distance of anterior chamfer.
4. Measure the height of the notch cut, meaning, the anterior posterior (AP) distance (notch surface).

Those measurements will be collected as well as the femoral implant size.

Calculations of surface area:

1. ML surface - will be calculated as ML distance - ML width of the implant. That number, will be than be multiplied by the combined length of the implant distal condyl and anterior chamfer.
2. Anterior surface - which is mostly a triangle shaped will be calculated as, ML distance of anterior chamfer (triangle base) times the triangle height which is distance from anterior chamfer edge to most proximal exposed bone on the anterior cut divided by 2. From that surface area, the implant anterior flange area will be deducted.
3. Notch surface - will be calculated as AP notch height X width of the notch. For implant size 2-5 there is the same notch width, and 6-10 have same notch width.

Combining the value of 1+2+3, is the overall exposed bone surface that needs bone wax coverage.

The exposed bone surface will be document by following grading system:

Grade 1: up to 3 millimeters (mm) of exposed bone

Grade 2: >3 to 6 mm exposed bone

Grade 3: >6 mm exposed bone

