6.3 MEASURES TO MINIMIZE BIAS: RANDOMIZATION AND BLINDING

The Biostatistics Unit will develop a randomization procedure using a permuted block design within the Biostatistics Randomization Management System (BRMS) system. Additional details of the procedure, including required record keeping, will be further developed upon approval of this protocol. The Biostatistics Unit has extensive experience in implementing and in producing detailed documentation for such procedures. The patient will be blinded to their randomization group.

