9 STATISTICAL CONSIDERATIONS

○ 9.1 STATISTICAL HYPOTHESES

- Primary Efficacy Endpoint(s):

The primary endpoint is estimated total blood loss measured on POD 1, as calculated by Hb-Balance formula. Blood loss is measured in the morning prior to receiving anticoagulant treatment. We hypothesize that applying bone wax during TKA will reduce blood loss on POD 1.

- Secondary Efficacy Endpoint(s):

The secondary endpoints are hemoglobin and hematocrit from preoperative to POD 1, as well as, the Knee Society Score (KSS), which is collected preoperatively and 8 weeks postoperatively. There are two KSS scores; namely, (1) the patient's self-assessment of pain, expectations and functional outcomes, as well as, (2) the surgeon's objective measurements.

We hypothesize that applying bone wax during TKA will reduce the quantity of change in hemoglobin and hematocrit from preoperative to POD 1.

We hypothesize that applying bone wax during TKA will positively impact KSS; namely, a reduction in pain, an increase in functional outcomes and an increase in alignment, range of motion and stability at 8 weeks postoperative.

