9.4.2 ANALYSIS OF THE PRIMARY EFFICACY ENDPOINT(S)

Estimated total blood loss on POD 1 will be compared between the treatment and control groups using a two-sample t-test. If the standard assumptions of Normally distributed residuals and equality of variance do not hold, then an appropriate transformation or non-parametric method will be used.

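### The primary analysis has no surgeon term, although the protocol treats surgical technique as a source of outcome variation; adding one is a small, nearly free gain in precision

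*Combined protocol and SAP*

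**What the plan says.** The synopsis (section 1.1) explains the choice of surgeons: "The restriction of this study to two surgeons will limit variations in the outcomes being measured due to differences in surgical technique". Section 2.1 repeats the statement. The primary outcome is blood loss: "The primary endpoint is estimated total blood loss measured on POD 1, as calculated by Hb-Balance formula" (section 9.1).

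On allocation, section 4.1 says "Patient stratification is not needed for the randomization" and gives no reason. Section 6.3 says "The Biostatistics Unit will develop a randomization procedure using a permuted block design within the Biostatistics Randomization Management System (BRMS) system"; it names no stratification factor and leaves further procedural detail for later.

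On analysis, section 9.4.2 says "Estimated total blood loss on POD 1 will be compared between the treatment and control groups using a two-sample t-test". Its fallback is a transformation or a non-parametric method, again with no covariate. The mixed models in section 9.4.3 name no surgeon term. Subgroup and exploratory analyses (sections 9.4.7 and 9.4.9) are marked not applicable.

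**The concern.** The design regards technique as important enough to limit who operates, yet two surgeons remain and neither the allocation nor the analysis takes account of which one operated. Section 6.1.2 also has the wax applied "as indicated by the surgical circumstances and the preference of the surgeon", so some variation between the two is foreseen.

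If the surgeons' average blood loss differs, that difference stays in the t-test's error variance. By chance, one arm may also hold more of one surgeon's patients. Section 9.2 fixes the sample size by feasibility, so precision can come only from the analysis. There is little to spare at the lower end of the 150 to 200 mL range that the investigators call clinically significant. Each patient is scheduled with one of the two surgeons, so the covariate should be known before randomization.

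**Working it through.** **Inputs from the documents.** 50 patients per arm, alpha 0.05, pooled SD 271.5 mL, differences of 153 and 200 mL (section 9.2). A two-sided test is taken because it reproduces the plan's table.

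**Inputs assumed.** The between-surgeon difference in mean blood loss, g, at 50 to 200 mL, and equal caseloads. The documents give neither.

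**1. The plan's own power table.** The pooled SD is √((282.7² + 259.8²)/2) = 271.5. The standard error of the difference is 271.5 × √(2/50) = 54.3 mL. The noncentral t with 98 df gives 79.7%, 95.4%, 82.3%, 91.0% and 80.8% for the five rows, against 80%, 95%, 82%, 91% and 81% stated. The table reproduces.

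**2. Power with a surgeon term.** If 271.5 mL is the total SD, the residual SD after fitting surgeon is √(271.5² − 0.25g²), with 97 df.

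| g (mL) | Residual SD (mL) | Share of variance | Power at 153 mL | Power at 200 mL |
|---|---|---|---|---|
| no term | 271.5 | – | 79.7% | 95.4% |
| 50 | 270.3 | 0.8% | 80.0% | 95.6% |
| 100 | 266.9 | 3.4% | 81.0% | 96.0% |
| 150 | 260.9 | 7.6% | 82.7% | 96.7% |
| 200 | 252.4 | 13.6% | 85.1% | 97.5% |

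At a 70:30 caseload (0.21g² in place of 0.25g²) power at 153 mL is 79.9%, 80.8%, 82.2% and 84.2%.

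These figures take the arms as balanced on surgeon. Without stratification the average squared correlation between arm and surgeon is 1/99, which multiplies the variance by 1/(1 − 1/99) = 1.010. Power at 153 mL is then about 79.6%, 80.6%, 82.3% and 84.7%, so the gain at g = 50 mL disappears.

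**3. Chance imbalance.** If the two surgeons' cases are fully interleaved along the list, one surgeon's count in one arm is hypergeometric (100, 50, 50). The chance that the arms differ by 10 or more of that surgeon's patients (30 against 20) is 7.1%. Such a split moves the estimate by (0.6 − 0.4) × g, which is 20 mL at g = 100 and 30 mL at g = 150. Relative to the standard error this is 20/54.3 = 0.37 to 30/54.3 = 0.55.

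The 7% depends on case order. Each complete block is half wax and half control, so if every block holds one surgeon's patients only, the gap is zero. Simulated runs of 3 or 4 consecutive cases per surgeon, with blocks of 4 or 6 (both assumed), give 0 to about 2% when the runs come in random order. Strictly alternating runs of 4 with blocks of 6 leave it near 7%.

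**4. If 271.5 mL is instead a within-surgeon SD.** The unadjusted SD becomes √(271.5² + 0.25g²), and unadjusted power at 153 mL falls to 79.3%, 78.3%, 76.7% and 74.5% for g = 50, 100, 150 and 200 mL.

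**The case against.** The strongest reply is that nothing is broken. A 1:1 randomized comparison by t-test is unbiased, and its standard error already covers chance imbalance in surgeon as in any other baseline factor. A reader might infer that the result is biased, or that imbalance enters the estimate unaccounted for; the documents support neither. This stands in full.

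Restriction to two surgeons at one hospital is itself the plan's control for technique. That stands in part, because the text says only that it "will limit variations in the outcomes being measured due to differences in surgical technique".

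A reader might also take the background remark that the tourniquet is "inflated to a pressure determined by the surgeon" as evidence that the two surgeons differ. It is a general description of the method, and section 4.2 says that blood-minimizing strategies, tourniquet included, will be consistent. Surgeon preference in applying wax can act only in the wax arm. That would be a treatment-by-surgeon interaction, which a main-effect term does not model. Neither passage measures a surgeon difference.

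Two practical points also stand. No section, including the schedule of activities in section 1.3, lists the operating surgeon as a collected item. And stratification has a cost: surgeons learn each allocation (section 6.4) and may take part in recruitment (section 5.5), so a surgeon-specific list would show each of them an entire block sequence.

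The deferral of detail in section 6.3 is no answer, since section 4.1 rules out stratification and nothing defers the choice of analysis model.

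**Conclusion.** The point holds as a free improvement of low severity. The plan acknowledges technique as a source of variation and then makes no use of surgeon in allocation or analysis.

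The gain at 153 mL is negligible if the surgeons differ by 50 mL, roughly 1 to 3 points for 100 to 150 mL, and about 5 points at 200 mL, which is more than the treatment effect itself. At a 200 mL treatment effect little remains to be gained. All of this rests on an assumed surgeon difference, an assumed caseload split and the reading of 271.5 mL as a total SD.

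The documents do not support calling the t-test invalid, the trial underpowered for want of this term, or stratification by surgeon a requirement.

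**What to change.** - **Section 9.4.2:** replace the unadjusted t-test with a prespecified linear model of POD 1 blood loss on arm and surgeon. Carry surgeon into the fallback: keep the term in a transformed model, or use a rank test stratified by surgeon.
- **Section 9.4.3:** add surgeon as a fixed effect in the hemoglobin, hematocrit and KSS models. If the treatment contrast is arm by visit, surgeon by visit is needed too for the term to act on change. Section 9.1 describes one KSS component as measured by the surgeon, so surgeon may there also be a rater effect.
- **Data collection:** list the operating surgeon as a study data item.

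Make these changes before any outcome is compared by arm. The cost is one degree of freedom in the primary model and one data field.

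Stratifying the permuted blocks by surgeon is optional, and only if enrolment has not started. It should use varying block sizes, which limit but do not remove predictability for unblinded surgeons. It must be paired with the model term: stratifying while keeping the unadjusted t-test would make that test conservative, with a true type I error of about 0.046 to 0.033 for surgeon differences of 50 to 200 mL at equal caseloads.
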